6.2.3 N and N-CTD binding IgG levels

- Estimands: geometric mean value
- Analysis set: 1/2/3-dose evaluable and expanded immunogenicity populations for SinoVac recipients
- Time points: before dose 1, before dose 2, 1 month after dose 2, 2 weeks after dose 3, 6, 18 and 36 months after vaccination
- Statistics: Geometric mean; % with value above LLOD
- Figure: column scatter dot plot with geometric mean and CI95 error bars
- Intercurrent events: Values below the LLOD will be set to 0.5 of the cut-off/limit for analysis.

6.2.4 GMR of N and N-CTD binding IgG in participants 11-17 years of age to those 18 years of age or above receiving CoronaVac

- Estimands: geometric mean ratios
- Analysis set: 1/2/3-dose evaluable and expanded immunogenicity populations
- Time points: 1 month after doses 1 and 2, 2 weeks after dose 3, 6, 18 and 36 months after vaccination; including cross-comparison of 1 month after dose 1 in adolescents and 1 month after dose 2 in adults and 1 month after dose 2 in adolescents and 2 weeks after dose 3 in adults
- Statistics: exponentiated difference in mean and CI95 on natural log scale for geometric means and two-sided CI95 (or one-sided CI97.5). For testing noninferiority.
- Figure: forest plot
- Intercurrent events: Values below the cut-off/lower limit of detection/quantification may be set to 0.5 of the cut-off/limit for analysis if applicable for the assay.

6.2.5 Correlates of immunogenicity

We explore the correlation between immunogenicity outcomes by Pearson correlation after logarithmic transformation. Participants with valid results for both variables will be included for correlation analysis between any two variables.

- Estimands: Pearson correlation coefficient
- Analysis set: 1/2/3-dose evaluable immunogenicity populations. Subgroup analysis is performed by vaccine type, dose number and age group.
- Time points: pre-dose 1, pre-dose 2 and 1 month after dose 2, 2 weeks after dose 3, 6, 18 and 36 months after vaccination
- Statistics: Pearson correlation after logarithmic transformation
- Figure: correlation matrix

6.2.6 GMR of S and S-RBD binding IgG, surrogate neutralizing antibody inhibition level, and neutralizing antibody titers, IgG avidity index and FcγRIIIa-binding IgG in participants 11 years or above of age living with diseases to those healthy receiving a particular vaccine

- Estimands: geometric mean ratio
- Analysis set: 2/3-dose evaluable and expanded immunogenicity populations
- Time points: 1 month after dose 2, 2 weeks after dose 3, 6, 18 and 36 months after vaccination
- Statistics: exponentiated difference in mean and CI95 on natural log scale for geometric means and two-sided CI95 (or one-sided CI97.5).
- Intercurrent events: Values below the cut-off/lower limit of detection/quantification may be set to 0.5 of the cut-off/limit for analysis if applicable for the assay.

6.2.7 GMR of responsive Th1 and Tc1 cell frequencies in participants 11 years or above of age living with diseases to those healthy receiving a particular vaccine

- Estimands: geometric mean ratio
- Analysis set: 2/3-dose evaluable and expanded immunogenicity populations
- Time points: 1 month after dose 2, 2 weeks after dose 3, 6, 18 and 36 months after vaccination
- Statistics: exponentiated difference in mean and CI95 on natural log scale for geometric means and two-sided CI95 (or one-sided CI97.5).
- Intercurrent events: Values below the cut-off/lower limit of detection/quantification may be set to 0.5 of the cut-off/limit for analysis if applicable for the assay.

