3.1.2 Immunogenicity endpoints

3.1.2.1 anti-S IgG levels

We measure SARS-CoV2 full S and S-RBD binding antibody level in sera as a primary immunogenicity endpoint. We report results as OD450 value. Values below the limit of detection will be taken as 0.5 of the lower limit of detection. **Geometric** mean OD450 values will be calculated for each timepoint in each subgroup.

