3.1.2.2 Surrogate neutralizing antibody inhibition level

We measure SARS-CoV2 S-RBD antibody ACE2-binding inhibition level in sera as a primary immunogenicity endpoint. We report results as level of inhibition (%). Values below the limit of quantification will be taken as 0.5 of the lower limit of quantification. **Geometric mean** inhibition percentage will be calculated for each timepoint in each subgroup.

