3.2.4 Correlates of immunogenicity

Correlations between primary immunogenicity outcomes will be evaluated by Pearson correlation coefficients after natural log transformation, with a more stringent significance level with lower alpha to account for multiple comparison testing. Relationships between immunogenicity outcomes and baseline variables such as age, sex and haematological parameters will be explored by multiple linear regression by vaccine type and age subgroup.

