6.1.2.4 S binding IgG avidity index

- Estimands: geometric mean value
- Analysis set: 1/2/3-dose evaluable and expanded immunogenicity populations
- Time points: before dose 1, before dose 2, 1 month after dose 2, 2 weeks after dose 3, 6, 18 and 36 months after vaccination
- Statistics: Geometric mean
- Figure: column scatter dot plot with geometric mean and CI95 error bars
- Intercurrent events: N/A.

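### At pre-dose 1, Pearson correlations between the half-limit-imputed antibody assays are undefined or driven by the few participants above the limit

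*SAP*

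**What the plan says.** SAP section 3.2.4 sets the method: "Correlations between primary immunogenicity outcomes will be evaluated by Pearson correlation coefficients after natural log transformation". Section 6.2.5 repeats it ("Statistics: Pearson correlation after logarithmic transformation") and lists the visits as "Time points: pre-dose 1, pre-dose 2 and 1 month after dose 2, 2 weeks after dose 3, 6, 18 and 36 months after vaccination". A pair enters on one condition: "Participants with valid results for both variables will be included for correlation analysis between any two variables". The results are then split: "Subgroup analysis is performed by vaccine type, dose number and age group". Section 6.2.5 has no rule for tied or censored values and no minimum number of detectable results.

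For S and S-RBD IgG, PRNT and FcγRIIIa-binding IgG, section 3.1.2 says "Values below the limit of detection will be taken as 0.5 of the lower limit of detection". Section 3.1.2.2 does the same for the surrogate neutralization assay: "Values below the limit of quantification will be taken as 0.5 of the lower limit of quantification". The rule is not universal. Section 6.1.2.4 has "Intercurrent events: N/A" for avidity, and section 6.1.2.6 replaces Th1/Tc1 frequencies only where they fall below the cut-off.

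In section 4.2, the two- and three-dose healthy evaluable sets admit participants shown to be seronegative or of unknown status. The single-dose healthy evaluable set also admits anyone without a known past infection. The evaluable sets for all participants, healthy or not, carry no serostatus condition.

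**The concern.** Before the first dose, a largely uninfected population should mostly read below the limit on SARS-CoV-2 antibody assays. After substitution, those participants share one value per assay. Pearson's r needs variance in both variables. With none it cannot be computed; with a handful of people off the floor, it mainly contrasts those people with everyone else. The condition on valid results does not remove the tied pairs, because a below-limit result is a valid result.

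At stake is how the baseline panel of the planned correlation matrix is read. A high, strongly significant coefficient there could be taken as agreement between assays, when it shows only that the same few people were positive on both. It could not describe a response to vaccine in any case. The stricter significance level in section 3.2.4 would not screen such cells out, since their p-values are extremely small.

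**Working it through.** The SAP gives no figure for this analysis, so there is none to reproduce.

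**Which pairs are affected.** The primary immunogenicity outcomes are S IgG, S-RBD IgG, surrogate neutralization, PRNT50, PRNT90, avidity, FcγRIIIa-binding IgG, Th1 and Tc1: 9 outcomes, 9 × 8 / 2 = 36 pairs. Six are antibody assays with the half-limit rule, giving 6 × 5 / 2 = 15 pairs. Avidity enters 8 pairs. The remaining 13 involve Th1 or Tc1 (2 × 6 + 1).

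**Inputs.** From section 5.1.2: SD s = 0.65 on the natural log scale and n = 61 per group. Assumed: k participants positive on both assays, their mean level, and zero correlation between the assays among them. Everyone else sits at ln(0.5 × limit).

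**Everyone at the floor on an assay.** r = cov(x, y) / (SD_x × SD_y) = 0/0, undefined.

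**A few participants above the floor.** Let p = k/n, and let d be the distance on the log scale from the floor to the mean of the positives. Then approximately

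r ≈ (1 − p)d² / [(1 − p)d² + s²(k − 1)/k].

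For n = 61, k = 3 and a mean 2.0 ln units above the limit: d = 2.0 + ln 2 = 2.69 and p = 0.049. The numerator is 0.951 × 7.25 = 6.90, the added term is 0.4225 × 2/3 = 0.28, and r ≈ 6.90/7.18 = 0.96. The true association among the positives is zero.

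**Simulation** (draws below the limit reset to the floor):

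| Setting | Median r (5th–95th percentile) |
|---|---|
| n = 61, mean +2.0 ln, k = 1 | 1.00 |
| same, k = 2 | 0.99 (0.88–1.00) |
| same, k = 3 | 0.97 (0.88–1.00) |
| same, k = 5 | 0.96 (0.88–0.99) |
| n = 61, weak positives (+0.7 ln), k = 3 | 0.85 (0.37–0.99) |
| same, k = 5 | 0.80 (0.46–0.96) |
| n = 61, +2.0 ln, k = 3, second assay detects half of them | 0.72 (0.41–0.99); undefined in 13% of runs |
| n = 61, +2.0 ln, k = 3, 10% of seronegatives above the limit | 0.67 (0.51–0.82) |
| same, 50% above the limit | 0.32 (0.13–0.49) |
| n = 61, k = 0, 10% above the limit | about −0.05 |

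With n = 100 and positives at a median of 5 times the limit, the median r is 0.98, 0.95 and 0.93 for k = 2, 5 and 10, with p < 0.001 in essentially every run.

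**Pairs outside the 15.** A tied antibody assay with k = 3 positives, against an unrelated continuous variable such as a T cell frequency, gives median r 0.00 (−0.21 to 0.21). Two T cell readouts, each about half above cut-off and with true correlation 0.5, give 0.44 (0.23–0.62).

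**Would keeping only above-limit pairs help at later visits?** Bivariate normal data, SD 0.65:

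| True r | Below limit, each assay | Half-limit substitution | Above-limit pairs only |
|---|---|---|---|
| 0.5 | 15% | 0.48 | 0.38 |
| 0.5 | 50% | 0.43 | 0.27 |
| 0.8 | 30% | 0.75 | 0.66 |
| 0.8 | 50% | 0.73 | 0.60 |

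Restriction truncates the range and is further from the truth than the SAP's own rule in every row.

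**The case against.** The best defence is that the high-r case needs previously infected people in the analysis set, and the SAP limits them. The two- and three-dose healthy evaluable sets are meant to exclude known baseline seropositives. Section 7.2 analyses paediatric patients with prior COVID-19 separately, and section 6.3 makes prior COVID-19 its own subgroup. Anyone with a baseline antibody result will seldom be of unknown serostatus. In those healthy sets the likelier outcome is an empty cell, which misleads nobody. This stands, and it moves the high-r case mainly to the evaluable sets for all participants and to the looser single-dose set, with unknown serostatus as a residual route.

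A reader might also infer that every baseline coefficient is undefined or close to 1, or that every seronegative participant carries the same value. The SAP supports neither. It states no assay limits and does not say that all seronegatives read below all of them. Avidity has no half-limit rule, and Th1/Tc1 are replaced only below cut-off, so 21 of the 36 pairs lie outside the argument. Nor does the check show that half-limit substitution does serious harm after vaccination: with up to 50% of values at the floor it pulled r down only modestly.

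Lastly, section 6.2.5 is a secondary exploration that feeds no decision rule in section 5.1.1. That is correct and limits the weight of the point.

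**Conclusion.** The point holds for correlations at pre-dose 1 between antibody assays that share the half-limit rule. There the coefficient is undefined or dominated by the few participants above the limit, and does not measure association between real values. It approaches 1 (about 0.93 to 1.00 in the simulations) only if the remaining participants are tied and the same people are clearly positive on both assays. Weaker positives, partial detection or background readings above the limit bring it to about 0.3 to 0.85, still spurious against a true value of zero. These sizes rest on assumed numbers and levels of positives. One of seven visits and 15 of 36 pairs are concerned. This is a minor point: no primary conclusion depends on it.

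**What to change.** In section 6.2.5, remove pre-dose 1 from the visits for pairs of half-limit-imputed antibody assays. If a baseline summary is wanted, report the proportion of participants above the limit on both assays. At later visits, keep all valid pairs, state how many values are at the floor for each pair and, where there are many, use a correlation that models left-censoring, such as a bivariate censored normal model. Do not restrict later visits to above-limit pairs, because that biases r toward zero.

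The cost is a line or two of SAP text, minor programming and the loss of one exploratory baseline panel for these pairs. No data collection changes.

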6.3 Subgroup analysis

As described elsewhere in this protocol, subgroup analyses include:

- age (18 years and above, 11-17 years, 3-10 years, and below 3)
- healthy history, conditions include:
 - Immune diseases
 - Combined defects
 - Humoral defects
 - Immune dysregulation
 - Innate defects
 - Phagocytic defects
 - Renal disorders
 - On immunosuppression only
 - On dialysis
 - Post-kidney transplant
 - Hematological conditions
 - Post-HSCT
 - Acute lymphoblastic leukemia
 - Allergy
 - To PEG-containing drugs
 - To first dose of COVID-19 vaccine
 - Neuromuscular disorders
 - Immune-mediated
 - Muscular dystrophy on immunosuppression
 - Prior COVID-19

6.4 Baseline and other summaries and analyses

6.4.1 Baseline

6.4.1.1 Demographics

Demographics will be summarized in the enrolled and healthy safety population.

6.4.1.2 Health characteristics

Count for a particular medical history (by MedDRA SOC and PT terms) will be listed when present in the enrolled population. Count and percentage for participants with at least one comorbid condition linked to severe COVID-19 illness will be listed in the enrolled and healthy safety population as well.

6.4.2 Study completion and participant disposition

6.4.2.1 Participant disposition summary

Summary of participant disposition will give the count for participants in age subgroups, for each stage of completion (received doses 1, 2 and 3, attended follow-up clinics, withdrew or excluded, with reason) in the enrolled and healthy safety population.

6.4.2.2 Blood sampling and e-Diary completion

Count and percentage of participants who gave blood samples in and out of pre-specified time windows and submitted reactivity and safety data will be given for each timepoint in the enrolled and healthy safety population.

6.4.3 Intervention

6.4.3.1 Vaccination timing and administration

Count of participants who received dosing in and out of pre-specified time windows will be given for each dose in the enrolled and healthy safety population.

6.4.4 Prior/concomitant vaccination and medications

Count of participants who were medicated or vaccinated 28 days before and after each dose will be given for each dose for each prior/concomitant medication/vaccine in the enrolled and healthy safety population.

7 Analysis timeline

Dependent on the progress of visits, interim analyses will be planned for different subgroups throughout the study period to report results of different timepoints.

7.1 Interim analysis 1 (Nov 2021)

Interim analysis will be performed first in November 2021 when most enrolled participants with kidney diseases, neurological diseases and hematological disorders or history of HSCT have completed post-dose 2 assessment under the age of 18 years for BioNTech.

The analysis will analyze the available immunogenicity data (S-RBD IgG levels and sVNT) by descriptive statistics without hypothesis testing. Reactogenicity and safety will also be described.

7.2 Interim analysis 2 (Jan 2022)

Interim analysis will be performed in Jan 2022 when 100 healthy participants have completed post-dose 2 assessment under the age of 18 years, including at least 50 for PRNT, for each vaccine.

While paediatric patients with prior COVID-19 and severe paediatric/immune conditions have been enrolled in this trial, the analysis of these participants will be separate. Safety, reactogenicity and immunogenicity analyses will focus on healthy participants.

Key objectives of this analysis are to describe the reactogenicity and safety of these vaccines in the pediatric age group, compare the acute immunogenicity of the vaccines in adolescents and adults, and compare the acute immunogenicity of the two vaccines in adolescents. We aim to demonstrate non-inferiority in a range of immunogenicity endpoints in adolescents to adults.

7.3 Interim analysis 3 (May 2022)

Interim analysis will be performed in May 2022 when more than 60 healthy adolescents receiving CoronaVac and 60 receiving BNT162b2 have completed post-dose 3 assessment under the age of 18 years, including at least 20 for PRNT for each vaccine. Reactogenicity and safety will be analyzed. Antibody and T cell responses against Omicron will also be evaluated.

7.4 Interim analysis 4 (May 2022)

Interim analysis will be performed in May 2022 when most participants with pediatric conditions have completed post-dose 3 assessment under the age of 18 years. Participants with kidney diseases, immune diseases, blood disorders and neurological disorders will be separately analyzed. Immune responses will be analyzed according to diseases subtypes, age, and vaccine regimen. Antibody responses against Omicron will also be evaluated. Reactogenicity and safety will be analyzed.
